1.4.2.5 Risks to Pregnancy

If potential participants are females who can become pregnant and want to take part in this study, they will be informed that PXVX0317 has not been thoroughly evaluated for potential risks to unborn or nursing children. Participants will be instructed not to get pregnant or breastfeed while taking part in this study. Female participants must have a negative pregnancy test at screening and again immediately before vaccination, however pregnancy tests are not 100% accurate. Participants will be advised that the only completely reliable methods of birth control are not having sex or surgical removal of the uterus. Other methods, such as the use of condoms, a diaphragm or cervical cap, birth control pills, IUD, or sperm killing products are not totally effective in preventing pregnancy.

If a participant becomes pregnant or feels she might be pregnant, she will be advised to contact her personal physician and the principal investigator of this study. If a participant becomes pregnant, the study team will ask permission to contact her regarding the outcome of her pregnancy.

1.4.2.6 Risks to Confidentiality

Efforts will be made to keep participants' personal health information confidential. In order to maintain confidentiality, paper study records will be stored in a secure location such as a locked office or locked cabinet. Electronic data will be password-protected. Electronic study records and samples taken will be coded with a number, not the participants' names. Records will only be shared with authorized personnel and only in connection with carrying out the obligations relating to the study.

Although efforts are made to protect the research study records, there is always a risk that someone could get access to the personal information in research records or other information researchers have stored about participants.

2 OBJECTIVES AND ENDPOINTS

2.1 Primary Objectives

The primary safety objective is to evaluate the safety of PXVX0317 when administered to prior alphavirus vaccine recipients versus gender and age-matched controls. Safety will be assessed by measuring the incidence of local and systemic solicited adverse events, unsolicited adverse events, and serious adverse events.

The primary immunogenicity objective is to evaluate the neutralizing antibody response to chikungunya virus induced by PXVX0317 when administered to prior alphavirus vaccine recipients versus gender and age-matched alphavirus naïve controls.

2.2 Secondary Objectives

The secondary immunogenicity objective is to evaluate the overall antibody responses to CHIKV and VEEV induced by vaccination with PXVX0317 when administered to prior alphavirus vaccine recipients versus gender and age-matched controls.

2.3 Exploratory Objectives

The exploratory immunogenicity objectives are to evaluate the cellular immune response to CHIKV induced by vaccination with PXVX0317 when administered to prior alphavirus vaccine recipients versus gender and age-matched controls, and to evaluate the humoral immune responses to EEEV and WEEV viruses induced by vaccination with PXVX0317 in selected subjects who previously received these vaccines versus alphavirus-naïve controls. Additional exploratory objectives are to collect human immunoglobulin for use in a mouse challenge study, and to evaluate the ability of CHIKV antibodies to PXVX0317 to neutralize diverse alphavirus strains.

2.4 Endpoints

2.4.1 Safety Endpoints

The safety and tolerability endpoints include local and systemic post-injection solicited events and other adverse events collected during the 7 days following the injection. Safety endpoints also include the occurrence of any unsolicited adverse events through Day 29, and serious adverse events and adverse events leading to withdrawal at any time during the study. All safety data will be tabulated according to pre-exposure status and at the time points of assessment.

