5.2 Early Discontinuation Visit

All subjects who discontinue study participation before the Day 182 visit will be requested to undergo an Early Discontinuation visit.

- AE evaluation if indicated (solicited if within 7 days of vaccination; unsolicited if within 28 days of vaccination);
- Collection and review of the Memory aid (if within 7 days of vaccination);
- Vital signs may be collected at the discretion of the investigator
- Clinical check;
- Blood Collection for:
 - CBC (if discontinuation occurs within 7 days of vaccination)

- creatinine, AST, ALT (if discontinuation occurs within 7 days of vaccination)
- Sera for antibody assays/future use.
- Urine pregnancy test for females of child-bearing potential (if discontinuation occurs before Day 29).

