6.5 Reporting of Adverse Events

6.5.1 Reporting Periods

The reporting period for solicited AEs begins immediately after the injection and continues for 7 days. The reporting period for unsolicited AEs begins immediately after study vaccine administration on Day 1 and continues for 28 days afterwards. AEs that correspond to solicited AE terms but occur outside of (or continue past) the solicited AE collection period are also collected through the unsolicited AE reporting period. The reporting period for SAEs begins at the time of informed consent and continues for the duration of study participation.

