6.7.3 Early Discontinuation for Safety Reasons

The Investigator or designee must report any early discontinuation from study participation or further vaccination for safety reasons (as determined by the Principal Investigator) to the MM or designee within 24 hours of discontinuation. Additional information regarding ongoing adverse events may be provided as a follow-up report.

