APPENDIX A: SCHEDULE OF EVENTS

Study Event ¹	Screen	Day 1	Day 8	Day 22	Day 29	Day 57	Day 113	Day 182	Early DC
Compliance Ranges	-60 to -1	NA	+3 days	±3 days	±3 days	±7 days	±10 days	±14 days	
Informed Consent	X								
Vital signs	X	XX ⁸	X	X	X	X ⁹	X ⁹	X ⁹	X ⁹
Review Inclusion/Exclusion Criteria	X	X							
Screening Medical History to include prior/concomitant medications	X								
Physical Examination	X								
Interim medical history, solicited ² and unsolicited ³ AEs, and concomitant medications		X	X	X	X				X
Memory aid distribution		X							
Memory aid collection and review			X						If < D8
Clinical check ⁴		XX ⁸	X	X	X	X	X	X	X
CBC ⁵	X	X	X						If < D8
Creatinine, AST, ALT ⁵	X	X	X						If < D8
Anti-HIV-1/2, Anti-HCV, HBsAg, HBcAb, HBsAb	X								
Urine pregnancy test ⁶	X	X			X				If < D29
Sera for antibody assays/future use ⁷		X	X	X	X	X		X	X
Collection of blood for Peripheral Blood Mononuclear Cells (PBMCs)		X	X		X	X		X	
Minimum volume of blood required	24.5 mL	84.5 mL	84.5 mL	17 mL	57 mL	77 mL	0 mL	77 mL	0 to 20 mL
Cumulative volume of blood required (approximate mL)	30	120	210	230	290	370	370	450	n/a
Vaccination		X							

¹ SAE's will be collected throughout the study

² Solicited AEs collected through Day 8 only.

³ Unsolicited AEs collected through Day 29 only.

⁴ Clinical checks: targeted physical exams based on AEs/SAEs identified

⁵ CBC, Creatinine, AST, ALT will be collected but the results will not be included in the database.

⁶ Urine pregnancy tests only for women of child-bearing potential.

⁷ Antibody assays vary with time point but include NT₈₀ to CHIKV, PRNT₈₀ to VEEV, total antibodies to CHIKV and VEEV, and exploratory assays of humoral immunity.

⁸ On vaccination day, vital signs and clinical checks will occur twice: before and 30 to 60 minutes after vaccination.

⁹ Vital signs may be collected at the discretion of the investigator past Day 29 but will not be included in the database.

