7.2. Adverse Events

An AE is any untoward medical occurrence in a study participant, regardless of the suspected causal relationship with study vaccine. An AE can therefore be a new-onset symptom or disease, an exacerbation of a pre-existing symptom or disease, a new-onset laboratory abnormality considered by the Investigator to be clinically significant, a new-onset symptom or disease that occurs as a result of a protocol-specified procedure.

The reporting period for SAEs begins at the time of informed consent and continues for the duration of study participation. The reporting period for solicited AEs begins after study vaccine administration on Day 1 and continues through Day 8. The reporting period for unsolicited AEs begins after study vaccine administration on Day 1 and continues through Day 29.

Solicited AEs are assigned to two different categories of events, systemic and local, with the following pre-specified signs and symptoms:

1. Systemic events: fever with oral temperature ≥ 100.4 °F, chills, malaise, fatigue, headache, myalgia, arthralgia, and nausea
2. Local events: pain, redness, and swelling at the injection site

Solicited AEs from Day 1 through Day 8 will be recorded on the solicited AE electronic case report form (eCRF). Symptoms experienced on Day 8 and continuing beyond Day 8 will be recorded on the AE eCRF with a start date corresponding to the first date the symptom was continuously experienced through Day 8.

An unsolicited AE is defined as an AE that is spontaneously reported by the subject or discovered by the Investigator.

Adverse Event Dictionary

AEs will be coded using the MedDRA version 20.1. SOC, High Level Group Term (HLGT), High Level Term (HLT), PT, and Lowest Level Term (LLT) will be attached to the clinical database.

All solicited AEs will be summarized according to severity grading scales defined in Sections 6.2 and 9.5.1 of the protocol; these range from “mild” to “potentially life-threatening.”

The analyses of solicited AEs (categorized as systemic or local) will be tabulated by maximum severity and study arm. In addition, solicited AEs ongoing after 7 days post-injection will be also recorded as unsolicited AEs. Frequencies and percentages of subjects experiencing each solicited AE will be presented by maximum severity.

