7.3. Safety Endpoints

The safety and tolerability endpoints include local and systemic post-injection solicited events and other AEs collected during the 7 days following the injection. Safety endpoints also include the occurrence of any unsolicited AEs through Day 29, and SAEs and AEs leading to withdrawal at any time during the study. All safety data will be tabulated according to study arm and at the time points of assessment.

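### AEs leading to withdrawal are a safety endpoint for the whole study, but a non-serious AE that starts after Day 29 and causes withdrawal has no required AE record

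*Protocol*

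**What the plan says.** **Endpoint.** Protocol 2.4.1 gives unsolicited AEs a window that closes at Day 29. It sets SAEs and "adverse events leading to withdrawal at any time during the study" apart with no day limit. SAP 7.3 does the same: "SAEs and AEs leading to withdrawal at any time during the study".

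**Collection.** Four places close the unsolicited AE window at Day 29:
- Protocol 6.5.1: "The reporting period for unsolicited AEs begins immediately after study vaccine administration on Day 1 and continues for 28 days afterwards".
- Protocol Appendix A, footnote 3: "Unsolicited AEs collected through Day 29 only". Table 1 in SAP 1.4 carries the same footnote.
- Protocol 5.2, on AE evaluation at the Early Discontinuation visit: "unsolicited if within 28 days of vaccination".
- SAP 7.2: "The reporting period for unsolicited AEs begins after study vaccine administration on Day 1 and continues through Day 29". The same section limits recording to events inside the reporting periods.

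Only SAEs have a longer window (Protocol 6.5.1): "The reporting period for SAEs begins at the time of informed consent and continues for the duration of study participation".

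**Outputs.** SAP Table 14.4.7 covers unsolicited AEs leading to withdrawal, and Table 14.4.11 covers the treatment-related ones. Neither title has a Day 29 limit, although most neighbouring unsolicited AE tables do. Item 13 of the AE overview in SAP 7.2.4 counts subjects with an AE leading to permanent discontinuation, also without a day limit.

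**The concern.** The endpoint and the collection rule have different time windows, and no reporting rule bridges them. A site that follows the reporting periods exactly would have no instruction to enter on the AE eCRF a non-serious AE that began on, say, Day 70 and made the subject leave. The disposition table could then show a withdrawal for an AE with no coded AE behind it. A reader of Table 14.4.7 could not tell whether no such event occurred or none was collected. With 30 subjects planned per arm, one missed event is 1/30 = 3.3% of an arm.

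**Working it through.** **Step 1. Check the study calendar.** Protocol 2.7 gives a maximum of 256 days per subject. Screening 60 + follow-up 182 + end-of-study window 14 = 256, so the stated figure is reproduced.

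**Step 2. Size the mismatch in time.** The endpoint runs to Day 182 and unsolicited AE collection to Day 29.
- Days outside collection: 182 − 29 = 153.
- As a share of study days from Day 1: 153/182 = 84.1%.
- As a share of the 181 days elapsed after Day 1: 153/181 = 84.5%.
- With the last visit 14 days early (Day 168): (168 − 29)/(168 − 1) = 139/167 = 83.2%.
- With the last visit 14 days late (Day 196): (196 − 29)/(196 − 1) = 167/195 = 85.6%.

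**Step 3. Take each kind of event behind a withdrawal after Day 29 and ask whether an AE record is required.**

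| Cause of withdrawal after Day 29 | Rule that applies | AE eCRF entry required? |
|---|---|---|
| SAE, any onset | Protocol 6.5.1 (whole of participation) and 6.6 (entry on the AE eCRF) | Yes |
| Non-serious AE, onset by Day 29 | Inside the 6.5.1 window, then followed under 6.4; SAP 7.2 assigns AEs by onset day | Yes |
| Non-serious AE, onset after Day 29 | Outside 6.5.1, Appendix A footnote 3, 5.2 and SAP 7.2 | Not by any of these rules |

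**Step 4. See whether the visit schedule closes the third row.** Protocol 5.1.3 to 5.1.5 (Days 8, 22 and 29) list both an AE evaluation and a clinical check. Sections 5.1.6 to 5.1.8 (Days 57, 113 and 182) list the clinical check only, and the AE row of Appendix A is blank at those visits. The schedule does not close it.

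**Step 5. See whether another reporting route closes it.** Under Protocol 6.7.3 the investigator or designee "must report any early discontinuation from study participation or further vaccination for safety reasons" to the medical monitor within 24 hours, with no day limit. That section does not ask for an AE eCRF entry, whereas 6.6 does so expressly for SAEs. The pre-evaluation database checks in 8.3.2 reconcile SAEs, and only SAEs, with the safety repository. SAP 4.3 summarizes the main reason for leaving early, but a disposition reason is not a coded AE with severity and causality. It cannot fill a table by system organ class and preferred term.

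**Step 6. Look for text that points the other way.** Protocol 6.5.2 tells the site to put every AE on the eCRF within three calendar days of learning of it, with no end date. Protocol 9.5.2 says that every unsolicited AE during the study is to be recorded. Read literally, both contradict the Day 29 limit. SAP 7.2 restates the 9.5.2 sentence with the reporting-period limit added.

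**The case against.** A reader might infer that the endpoint cannot be captured at all after Day 29, or that the withdrawal tables must read zero from then on. The documents do not support either inference. The first two rows of the table in Step 3 remain open to Day 182, so a withdrawal on Day 60 caused by an SAE, or by an AE that began on Day 25, can appear in the tables.

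The best case for leaving the text alone has three parts. First, the endpoint sentence can be read as a specific rule that overrides the general Day 29 window, and 6.5.2 and 9.5.2 fit that reading. The untruncated titles of Tables 14.4.7 and 14.4.11 suggest that this was the intention. Second, 6.7.3 does not say that the event stays out of the eCRF. Third, each subject receives one injection, on Day 1, so there is no later dosing to stop. Late withdrawals for non-serious AEs may be few, and no power figure or hypothesis test depends on them.

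The third part stands and limits the importance of the point. The first shows what the authors probably meant, but it leaves the plan contradicting itself. The operational instructions (reporting period, schedule footnote and discontinuation visit) all say Day 29, and two sites could reasonably act differently. On the second, silence in 6.7.3 does not create an eCRF duty that 6.5.1 has ended.

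**Conclusion.** The plan is wrong as written, in a narrow respect. For one class of event, non-serious AEs with onset on Days 30 to 182 that lead to withdrawal, the stated endpoint has no matching requirement for an AE record. Tables 14.4.7 and 14.4.11 and item 13 of the AE overview could therefore undercount. The exposed period is 153 of 182 study days (84%; 83.2% to 85.6% of post-vaccination time across the Day 182 visit window). This measures calendar time only. The documents give no expected number of such withdrawals, so the number of missed events cannot be estimated.

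The conclusion assumes that sites follow the reporting periods and schedule rather than the unlimited wording of 6.5.2 and 9.5.2, and that no eCRF guideline outside these documents adds the missing instruction. It also assumes that AEs already recorded can be flagged as the cause of withdrawal; the item list in 6.5.2 does not name such a field. The primary analysis and sample size are unaffected.

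**What to change.** **If collection is still open:** amend Protocol 6.5.1, 5.2 and Appendix A footnote 3, and SAP 7.2 with its Table 1 footnote, so that any AE leading to withdrawal is entered on the AE eCRF through Day 182 whatever its onset day. Reconcile 9.5.2 and 6.5.2 with 6.5.1. The cost is wording: the clinical checks at Days 57, 113 and 182, the Early Discontinuation visit and the AE eCRF already exist.

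**If collection is complete,** which is likely because the SAP addendum removing tables describes a decision made after database lock: define the reported endpoint as SAEs leading to withdrawal at any time plus non-serious AEs leading to withdrawal with onset by Day 29. Apply this to Tables 14.4.7 and 14.4.11 and item 13 of the overview, and state it in a footnote. Compare the disposition reasons and the 6.7.3 reports with the AE records, and describe in text any AE-related withdrawal that has no matching AE entry. With about 60 subjects this is a short listing check.

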2.4.2 Primary Immunogenicity Endpoint

The anti-CHIKV seroconversion rate at Day 22 in prior alphavirus vaccine recipients versus alphavirus-naïve controls, where seroconversion is defined as a 4-fold rise over baseline in anti-CHIKV neutralizing antibodies as determined by a luciferase-based assay (NT₈₀). This time point was chosen based on data from an on-going phase 2 study of this vaccine candidate (EBSI-CV-317-001) in which the peak neutralizing antibody response for other single-dose regimens was observed to occur on study Day 22.

2.4.3 Secondary Immunogenicity Endpoints

- Anti-CHIKV neutralizing antibodies, determined by luciferase-based assay (NT₈₀), in prior alphavirus vaccine recipients versus alphavirus-naïve controls, assessed by
 - Geometric mean titer (GMT) and geometric mean ratio (GMR) on Days 1, 8, 22, 29, 57 and 182.
 - Seroconversion rates on Days 8, 29, 57 and 182.
 - The proportion of subjects with titers of at least 40, 160 or 640 on Days 1, 8, 22, 29, 57 and 182.
- Anti-CHIKV total antibodies, determined by immunoassay, in prior alphavirus vaccine recipients versus alphavirus-naïve controls, assessed by
 - GMT and GMR on Days 1, 22 and 29.
 - Seroconversion rate on Days 22 and 29, where seroconversion is a 4-fold rise in titer over baseline.
 - The proportion of subjects with titers of at least 40, 160 or 640 on Days 1, 22 and 29.
- Anti-VEEV total and neutralizing antibody, as determined by an immunoassay and a Plaque-Reduction Neutralization Test (PRNT₈₀) respectively, in prior alphavirus vaccine recipients versus alphavirus-naïve controls, assessed by
 - GMT and GMR on Days 1, 22 and 29.
 - Seroconversion rate on Days 22 and 29, where seroconversion is a 4-fold rise in titer over baseline.
 - The proportion of subjects with titers of at least 40, 160 or 640 on Days 1, 22 and 29.

2.4.4 Exploratory Immunogenicity Endpoints

- Cellular Immune Responses to Chikungunya Antigens: PBMCs will be collected on Days 1, 8, 29, 57 and 182 in order to determine the nature and stability of the cellular immune response to PXVX0317.
- Humoral immune responses at other time points, to other pathogens (including EEEV and WEEV) and using other thresholds than those specified above may be performed in selected subjects.

[figure not shown]
- Neutralizing antibody titers to alphaviruses will be measured at three time points (Day 1 (pre-vaccination), Day 22, and Day 182).

STUDY PLAN

2.5 Study Design

This is a Phase 2 parallel-group age- and gender-matched open label study in healthy adults 18-65 years of age (Figure 3).

Figure 3: EBSI-CV-317-002 Study Schema

2.6 Number of Study Participants

The study population will be composed of 60 healthy adults, 30 of which have previously received an investigational heterologous alphavirus vaccine and 30 age- and gender-matched controls who meet the eligibility criteria listed in [Section 2.8](#). This number is based on the estimated number

of such individuals available for recruitment through the Fort Detrick Special Immunizations Program at USAMRIID. Replacements are allowed for subjects who drop out prior to Day 29. Refer to Section 4.18 for further details.

2.7 Estimated Study Duration

The study consists of a 60-day screening period, a treatment and observation period from Day 1 through Day 29, and a follow-up period through Day 182 (± 14 days). Therefore, the maximum possible study duration for an individual subject is 256 days.

2.8 Study Population

2.8.1 Inclusion Criteria

Subjects must meet all of the following criteria in order to be enrolled:

1. Age 18 to 65 years old (inclusive)
2. For women of childbearing potential, a negative pregnancy test at screening and on vaccination day, practicing highly effective contraception for at least 30 days prior to vaccination, and willing to use a highly effective method of contraception through study completion.
3. Able and willing to provide informed consent for study participation prior to screening procedures.
4. Free of obvious health problems as established by medical history and clinical examination at screening and enrollment.
5. Available to participate for the duration of the study (approximately 8 months).
6. For the cohort of prior alphavirus vaccine recipients, a documented history of prior alphavirus vaccination.

2.8.2 Exclusion Criteria

Subjects who meet any of the following criteria cannot be enrolled:

1. Acute disease or febrile illness at the time of enrollment.
2. Clinically significant cardiac, respiratory, rheumatologic or other medical or psychiatric condition that, in the opinion of the Investigator, places the subject at increased risk or affects their ability to understand and comply with study procedures.

3. Abnormal screening lab test results that, in the opinion of the investigator, obscures interpretation of the safety data or suggests a clinically significant cardiac, respiratory, rheumatologic or other medical condition that places the subject at increased risk.
4. Pregnant, lactating or planning to become pregnant during the study period.
5. Laboratory evidence of infection with Hepatitis B, C or HIV.
6. History of naturally (non-laboratory) acquired chikungunya or other alphavirus infection or travel to a WHO-designated chikungunya-endemic region within 30 days prior to Day 1.
7. History of acute allergic reaction to any component of CHIKV-VLP vaccine, or Alhydrogel®.
8. Current (30 days prior to Day 1) or anticipated use of systemic immunomodulatory or immunosuppressive medications.
9. History of splenectomy, immunosuppressive condition, autoimmune disease, or immunodeficient condition.
10. Family history of congenital or hereditary immunodeficiency.
11. Suspected or known current alcohol abuse that, in the opinion of the investigator, would interfere with their ability to understand and comply with study procedures.
12. Current intravenous drug use.
13. Prior receipt of an investigational chikungunya vaccine.
14. Receipt or planned receipt of any licensed vaccine from 30 days prior to Day 1 through the Day 29 study visit.
15. Participation in another clinical trial during the study period in which an investigational product is administered.
16. For the alphavirus naïve group, history of prior alphavirus vaccination is exclusionary.

